### AUC0-∞ (h·pg/mL)

$AUC_{0-∞}$  will be calculated as:

$$AUC_{0-∞} = AUC_{0-t} + \frac{C_{\text{last}}}{\lambda_z}$$

Where  $C_{\text{last}}$  is the last concentration used in the calculation of  $AUC_{0-t}$ .

### AUC%extrap (%)

$AUC\%_{\text{extrap}}$  will be calculated as:

$$AUC\%_{\text{extrap}} = 100 * \frac{AUC_{0-∞} - AUC_{0-t}}{AUC_{0-∞}}$$

### CL/F (L/h)

$CL/F$  will be calculated as:

$$CL/F = 1000^2 * \frac{\text{Dosage in mg}}{AUC_{0-∞}}$$

	EP-104IAR-201 Statistical Analysis Plan	Version: Final 1.0
	Date: 14-Jun-2023	Page 32 of 38

Where dosage is the actual dosage calculated from the residual EP-104IAR in the used injection kits.

### Vz/F (L)

Vz/F will be calculated as:

$$V_z/F = \frac{CL/F}{\lambda_z}$$

## 4. DATA HANDLING

### 4.1 Screening, Baseline, Pre-Dose, and Study Visits

Except for PK and WOMAC data, which will be analyzed at the actual sampling times, all other analyses will be presented based on the planned schedule of assessments in the protocol and recorded on the eCRFs and ePRO devices.

WOMAC pain post-baseline data (including subscale and associated questions) will be analyzed based on actual week from dosing per the mapping rules below:

Actual Week	Target Day	Study Day Range
Week 1	Day 8	7-13
Week 2	Day 15	14-20
Week 3	Day 22	21-27
Week 4	Day 29	28-34
Week 5	Day 36	35-41
Week 6	Day 43	42-48
Week 7	Day 50	49-55
Week 8	Day 57	56-62
Week 9	Day 64	63-69
Week 10	Day 71	70-76
Week 11	Day 78	77-83
Week 12	Day 85	84-90
Week 13	Day 92	91-97
Week 14	Day 99	98-104

Week 15	Day 106	105-111
Week 16	Day 113	112-118
Week 17	Day 120	119-125
Week 18	Day 127	126-132
Week 19	Day 134	133-139
Week 20	Day 141	140-146
Week 21	Day 148	147-153
Week 22	Day 155	154-160
Week 23	Day 162	161-164
Week 24	Day 169	165-174

WOMAC stiffness, WOMAC function, and WOMAC total post-baseline data (including subscales and associated questions) will be analyzed based actual week from dosing per the mapping rules below:

Actual Week	Target Day	Study Day Range
Week 4	Day 29	7-43
Week 8	Day 57	44-71
Week 12	Day 85	72-99
Week 16	Day 113	100-127
Week 20	Day 141	128-155
Week 24	Day 169	156-183

If more than one WOMAC data point is mapped to the same actual week, the one data point that is closest to the target day at the time of dosing will be used. Any data points that fall outside the windowing study day range will not be used.

Unless stated otherwise, baseline will be the last non-missing value, including unscheduled, prior to study drug administration. See Section 3.7 for the definition of baseline WOMAC pain. For efficacy data that are collected daily (NPRS scores, rescue medication usage, and physical activity levels), baseline is defined as the average of the available 7 days prior to dosing. Screening, when summarized, will be the last non-missing value, including unscheduled, that is prior to the day of study drug administration.

	EP-104IAR-201 Statistical Analysis Plan	Version: Final 1.0
	Date: 14-Jun-2023	Page 34 of 38

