9.2.5.7 Visit 9 (Week 24, Day 169 ±7 days) End-of-Study/Early Exit Visit

The following assessments will be performed at this visit:

- Blood samples for hematology, clinical chemistry, HbA1c, cortisol and PK analyses.
- Urine collection for safety urinalysis, pregnancy test and drugs of abuse.
- **Selected subjects only** - ACTH stimulation test.
- Vital signs.
- Physical exam.
- Exam of Index knee.
- Weight.
- PtGA.
- MDGA.
- WOMAC Index.
- Heath status (SF-36).

- Recording of AEs and changes in conmed use.
- Rescue medication accountability will be performed and unused medication collected.
- Check and collect ePRO device.
- The subject and the blinded Assessor will each be asked which treatment they believe was administered.

Imaging Sub-study (Week 24, Day 169 +14 days)

- Review MRI eligibility criteria
- Urine collection for pregnancy test (if applicable)
- MRI

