### 3.7 Primary Endpoint Analysis

The primary efficacy endpoint is the difference in change from baseline between EP-104IAR and vehicle in WOMAC Pain at Week 12, in the ITT population. Baseline WOMAC Pain will be calculated at the individual level and is defined as the average of no more than three pre-dose measurements including the three scheduled measurements: 2 measurements during the Washout and Baseline Period and 1 at Visit 2 (pre-dose). If the subject has less than three pre-dose measurements, the average of all available pre-dose measurements will serve as the subject's baseline value. If a subject has more than three pre-dose measurements, then the three measurements collected immediately prior to pre-dose will be used to derive baseline WOMAC pain and earlier measurements will not contribute.

Change from individual pre-dose baseline will then be calculated for each post-dosing weekly assessment from Week 1 through Week 24. A mixed-effects model for repeated measures (MMRM) model will then be fit to the change from baseline data for all subjects in the ITT population, including fixed effects terms for: site (potentially grouped, see Section 4.2 for more details); individual baseline WOMAC Pain; and the treatment-by-week interaction, where treatment and week are both defined as categorical variables. A random per-patient intercept will also be included. An unstructured covariance matrix at the patient level will initially be fit; if this model fails to converge numerically, a compound symmetry structure will be used.

No imputation of missing data will be performed for this analysis; the MMRM model allows handling of missing data under the assumption that data is missing at random (MAR). To assess robustness to the assumption that data is missing at random, a multiple imputation approach will be used. Under this approach, outcome data will be imputed according to the following logic:

	EP-104IAR-201 Statistical Analysis Plan	Version: Final 1.0
	Date: 14-Jun-2023	Page 18 of 38

- If missing data is due to lack of efficacy (as captured by the Study Termination page on eCRF), data will be imputed as if subjects received placebo.
- If missing data is due to other reasons, data will be imputed as if subjects received their actual treatment.

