#### 4.4 Unscheduled Data

Except for ACTH stimulation test results as described below, data obtained from unscheduled assessments (which also includes early exit visits) will only be considered for baseline determination; otherwise, unscheduled data will not be used in summary tables or included in the analyses. All unscheduled data will be presented in the listings.

ACTH stimulation test results will be mapped via the windowing rules in the below table. When more than one result for a subject occurs within one visit window, the worst result (i.e., Fail) will be mapped to that visit.

Visit (Mapped)	Target Day	Study Day Range
Screening		<1
Week 1	Day 3	1-9
Week 2	Day 15	10-22
Week 4	Day 29	23-43
Week 8	Day 57	44-71
Week 12	Day 85	72-106
Week 18	Day 127	107-148
Week 24	Day 169	149+

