#### 4.5 WOMAC Score Derivations

The WOMAC subscale scores are going to be calculated as follows:

**Pain Subscale Score:** It is defined as the average of 5 pain related questions (labeled in data as Section A). The pain score will be calculated if there are at least 4 available data points, and the score will be based on the average of the available data points. If there are 2 or more of the data points are missing, then the pain score will be missing.

**Stiffness Subscale Score:** It is defined as the average of 2 stiffness related questions (labeled in data as Section B). The stiffness score will be calculated if there is at least 1 available data point, and the score will equal the available data point. If both data points are missing, then the stiffness score will be missing.

**Function Subscale Score:** It is defined as the average of 17 function related questions (labeled in data as Section C). The function score will be calculated if there are at least 14 available data points, and the score will be based on the average of the available data points. If there are 4 or more of the data points are missing, then the function score will be missing.

	EP-104IAR-201 Statistical Analysis Plan	Version: Final 1.0
	Date: 14-Jun-2023	Page 36 of 38

**Total Score:** If any of the subscale scores are missing, then the total score will also be missing. Otherwise, total score will be calculated as the average of the 3 subscale scores. If any of the subscales were calculated in the presence of the missing data point, then the missing data point will first be imputed as the average of the rest of the questions within that scale, and then the total score will be calculated.

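### A completer whose Visit 9 falls on Days 162–164 is on protocol but can have no Week 24 WOMAC Pain score, because the Pain window opens only on Day 165

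*SAP*

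**What the plan says.** **Protocol.** Section 9.2.5.7 is headed "Visit 9 (Week 24, Day 169 ±7 days) End-of-Study/Early Exit Visit", so the permitted days are 162 to 176. The WOMAC Index is listed among that visit's assessments, and the ePRO device is checked and collected. Section 4.1 adds that no efficacy assessments follow Visit 9, even for imaging sub-study participants.

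**SAP 4.1, Pain.** WOMAC data are assigned to weeks by actual study day, not by nominal visit: "WOMAC pain post-baseline data (including subscale and associated questions) will be analyzed based on actual week from dosing per the mapping rules below". The last rows of the Pain table are Week 23 (target Day 162, Days 161–164) and Week 24 (target Day 169, Days 165–174). If two entries fall in one window, "the one data point that is closest to the target day at the time of dosing will be used". Also, "Any data points that fall outside the windowing study day range will not be used".

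**SAP 4.1, other scales.** Function, Stiffness and Total have their own table, in which Week 24 is Days 156–183. On Total, SAP 4.5 says: "Otherwise, total score will be calculated as the average of the 3 subscale scores". Pain is one of the three.

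**Status of the endpoint.** Change from baseline in WOMAC Pain at Week 24 is the third key secondary endpoint in the hierarchical sequence of SAP 3.8.1. It is analysed like the primary, with a mixed model for repeated measures (MMRM) on Weeks 1–24 and no imputation.

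**The concern.** The protocol's end-of-study window and the SAP's Week 24 Pain window do not match at the early end. A subject seen on Days 162–164 has kept to the schedule and answered the Pain items at the final visit. That score is labelled Week 23, and because the device has been returned no later entry can exist. No rule in the SAP assigns the Visit 9 record to Week 24.

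The treatment of the questionnaire is also uneven. On those days its Function, Stiffness and Total scores are Week 24, and the Pain answers contribute to Week 24 Total, yet they are not a Week 24 Pain score.

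At stake is information on an alpha-controlled endpoint. The MMRM recovers part of it from earlier weeks. The single-week Week 24 analyses cannot: the subgroup ANCOVAs of SAP 3.8.3 and the Pain responder tests of SAP 3.8.2. For Week 24 strict responders, defined on Pain or Function, the SAP sets only discontinued patients to non-responder and does not address a completer without a Pain score.

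**Working it through.** **Step 1: the plan's own figure.** Inputs from Protocol 11.2 and SAP 3.3: difference 0.8, SD 2.2, two-sided 5%, power 80%.

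- n per arm = 2 × (1.960 + 0.842)² × 2.2² / 0.8² ≈ 119, which agrees with the stated 120 or so.
- With 120 per arm, SE = 2.2 × √(2/120) = 0.284 and power = Φ(0.8/0.284 − 1.96) = 80.4%.
- 120 / 0.8 = 150 randomized per arm, as stated.

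These figures were set for Week 12 and are used below only for scale.

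**Step 2: map each permitted Visit 9 day.**

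| Visit 9 day | Pain assigned to | Function, Stiffness, Total assigned to |
|---|---|---|
| 162, 163, 164 | Week 23 | Week 24 |
| 165 to 174 | Week 24 | Week 24 |
| 175, 176 | no week, not used | Week 24 |

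Only on Days 162–164 is the device returned before the Week 24 window opens. On Days 175–176 the subject has held the device throughout Days 165–174, so a weekly home entry near Day 169 will usually fill Week 24.

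**Step 3: what happens to the early score.** It is normally kept as Week 23. It is dropped only if another Pain entry lies closer to Day 162, for example a home entry on Day 162 with Visit 9 on Day 163 or 164.

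**Step 4: share affected (assumed).** The documents give no distribution of Visit 9 dates. Taking a normal distribution restricted to Days 162–176, share = P(161.5 < day < 164.5) / P(161.5 < day < 176.5).

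| Assumed Visit 9 dates | Share on Days 162–164 | Subjects per 120 |
|---|---|---|
| mean 169, SD 1 | about 0% | 0 |
| mean 169, SD 2 | 1.2% | 1–2 |
| mean 169, SD 3 | 6.1% | 7 |
| mean 169, SD 4 | 10.6% | 13 |
| mean 167, SD 2 | 10.3% | 12 |
| uniform over 15 days | 3/15 = 20% | 24 |

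These are illustrations, and the last is not an upper bound: mean 166 with SD 3 gives 25.9%.

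**Step 5: loss of precision under the MMRM.** If a share p lacks Week 24, and earlier weeks explain a proportion R² of Week 24 variance, then n_eff = 120 × (1 − p) / (1 − R² × p), and the SE is multiplied by √(120 / n_eff). The correlation r is assumed to be 0.7 to 0.9. Two cases are shown:

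- recovery through Week 23 only: R² = r², i.e. 0.49 to 0.81
- all 23 earlier weeks equally correlated with each other and with Week 24: R² = 23r² / (1 + 22r), i.e. 0.687 to 0.896

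| Share p | SE rise, Week 23 only | SE rise, all earlier weeks |
|---|---|---|
| 1.2% | 0.1–0.3% | 0.1–0.2% |
| 6.1% | 0.6–1.7% | 0.3–1.0% |
| 20% | 2.3–6.2% | 1.3–3.8% |

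Example: p = 0.0614 and r = 0.7 give n_eff = 120 × 0.9386 / (1 − 0.49 × 0.0614) = 116.1, and √(120/116.1) = 1.017.

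**Step 6: in power terms.** Applying the Week 23-only range at a 6.1% share to Step 1 takes power from 80.4% to between 79.9% and 79.1%. At a 1.2% share the loss is about 0.2 points or less.

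**The case against.** The strongest defence is that the boundary looks deliberate and follows the actual-day principle. Weeks 1–22 all run from one day before target to five days after. On that pattern Week 24 would open on Day 168; the SAP shortens Week 23 and opens Week 24 on Day 165. The midpoint between targets 162 and 169 is Day 165.5, so Days 162–164 are nearer the Week 23 target. A score taken on Day 162 is, by calendar, a Week 23 score.

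Much of this stands. Labelling by actual day is legitimate, and so are wider windows for scales collected every four weeks. But the SAP has already given up its regular pattern to move Days 165–167 into Week 24. Whatever the reason, the move stops three days short of the protocol's window and leaves some on-protocol completers without the endpoint.

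It is also fair that Week 24 Pain is tested formally only if the primary and two earlier key secondaries succeed, and that the size rests on assumed visit dates. Protocol 9.2.5 asks that visits ideally fall on the same day of the week, so a smooth spread is only a convenience.

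A reader might infer that the plan throws this score away. On Days 162–164 it normally does not: the score enters the same MMRM as Week 23. Non-use by window applies on Days 175–176, where a home entry usually stands in.

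**Conclusion.** The mismatch is certain; its size is not. A completer seen on Days 162–164 has no Week 24 Pain score, and the consequence is a small loss of precision and power for one key secondary endpoint. If 1–6% of completers are affected, the SE rises by about 0.1–1.7%. That assumes Visit 9 dates centred on Day 169 with SD 2–3 days and a correlation of 0.7–0.9. Earlier or more dispersed visits would make it larger.

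Three stronger conclusions might be drawn, and the documents do not support them:

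- **Bias.** Nothing links an early Visit 9 to treatment or outcome. Affected subjects stay in the MMRM with their earlier weeks. If the SAP 3.7 multiple imputation is also run at Week 24, its rule for them is "If missing data is due to other reasons, data will be imputed as if subjects received their actual treatment".
- **A large loss of power.** Five of the 15 permitted days lie outside the Pain window, but two of those rarely cost a Week 24 value. Counting three days in 15 as lost and ignoring earlier weeks would give 96 per arm and 71.2% power. That needs uniform visit dates and a complete-case analysis, and the latter is not what is planned.
- **Harm to the primary.** The device is kept after Visit 7, so weekly home entries can still fill Week 12.

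This is a cheap improvement of low priority.

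**What to change.** Add to SAP 4.1, before unblinding:

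> For a subject who completes the study and has no Pain entry on Days 165–174, the Pain score from the WOMAC Index completed for Visit 9 within Days 162–176 is assigned to Week 24 and is not also used for Week 23; otherwise the closest-to-Day-169 rule applies.

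Leave the other windows as they are. The rule does not look at outcomes and displaces no in-window score. Limiting it to completers keeps it in line with SAP 4.4, under which "data obtained from unscheduled assessments (which also includes early exit visits) will only be considered for baseline determination".

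The cost is one mapping rule and its programming, with three downsides:

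- The timing of Week 24 scores is more spread out; a score from Day 162, the Week 23 target day, can be labelled Week 24.
- Week 23 is occasionally missing, when the Visit 9 entry is the only one on Days 161–164. Week 23 Pain is an additional secondary endpoint outside the hierarchy.
- When a home entry falls just before Visit 9, two scores a day or two apart are modelled as Weeks 23 and 24.

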## 4.2 Site Grouping Strategy

In some analyses site will be used as a covariate, and in these cases, sites will be pooled within country by size, smallest to largest, until there are at least 16 subjects from within the ITT population included in each pooled group.

## 4.3 Missing Data

Handling of missing data for assessing the primary and secondary endpoints is discussed in Sections 3.7, 3.8 and 4.5. Handling of plasma/serum values that are BLQ with respect to the pharmacokinetic analyses are described in Section 3.9. Additional considerations include:

- For the derivation of duration of symptoms in the index knee (years) and time since diagnosis in the index knee (years), partial dates will be imputed with the following rules:
  - When only the year is available (both month and day are missing), then the month will be imputed as July and the day will be imputed as 1.
  - When the month and year are available (only day is missing), then the day will be imputed as 15.
  - When only the year is available and it is the same year as administration of study drug, the duration in days will be calculated as the day of the year study drug was administered divided by two.
- Intermittent missing ePRO-collected diary data for rescue medication, activity levels and daily pain (NPRS) for post-baseline weeks will be imputed in instances when less than 4 entries are available at a given week. Last observation carried forward (LOCF) will be applied to carry forward the most recent post-baseline diary entries so that 4 entries are made available at a week. For example, if a subject has only 1 entry at a given week, the 3 most recent entries from previous post-baseline weeks will be carried forward to compute a weekly average out of 4 days. Similarly, if a subject has only 3 entries at a given week, only the 1 most recent entry from previous weeks will be carried forward to compute a weekly average out of 4 days.
- For the SF-36 survey, PRO CoRE will be used to impute missing values via proration, whereby the missing responses will be replaced with the mean of the observed scores of the completed questions within the same scale (per subject and timepoint). PRO CoRE will only be used in instances where at least  $\frac{1}{2}$  items in each of the eight scales are non-missing. If less than  $\frac{1}{2}$  items are completed within a scale or the complete scale or survey is missing, no imputation will be applied.

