### 3.8.2 Additional Secondary Efficacy Endpoints

All other efficacy data (WOMAC subscales, total WOMAC, NPRS, PtGA, MDGA, SF-36) will be listed and summarized in tables using standard summary statistics by treatment group. Exploratory analyses will be performed to identify key features of the efficacy profile. Analyses of these additional secondary endpoints will be based on the ITT population.

The following additional secondary endpoints will be assessed:

- Difference in change from baseline between treatment groups in WOMAC Pain at Weeks 1-11 and 13-23
  - This analysis will be identical to the primary analysis.
- Difference in change from baseline between treatment groups in WOMAC Pain Q1 (pain on walking) at Weeks 1-24
  - This analysis will be identical to the primary analysis.
- Difference in change from baseline between treatment groups in average daily NPRS at Weeks 1-24
  - This analysis will be identical to the primary analysis.
  - Average daily NRPS at Week 1 is defined as the average of non-missing NPRS pain scores from Day 1 through 8. For subsequent Weeks, average daily NPRS is defined as the average of the 7 days of non-missing daily NPRS data, allowing for the 8 day Week 1 (for example, Week 2 would be Days 9 through 15).
  - Baseline NPRS is defined as the average of the seven non-missing days immediately prior to dosing (Day 1).
- Difference in change from baseline between treatment groups in WOMAC Function at Weeks 4, 8, 16, 20 and 24
  - This analysis will be identical to the primary analysis.
- Difference in change from baseline between treatment groups in WOMAC Stiffness scores at Weeks 4, 8, 12, 16, 20 and 24
  - This analysis will be identical to the primary analysis.
- Difference in change from baseline between treatment groups in WOMAC Total scores at Weeks 4, 8, 12, 16, 20 and 24
  - This analysis will be identical to the primary analysis.
  - WOMAC Total is defined as the average of the three subscale scores (Pain, Stiffness, and Function).
- Difference between treatment groups in time to return to baseline WOMAC Pain

- This will be analyzed using a Cox proportional hazards regression with treatment, site (possibly grouped; see Section 4.2), and baseline WOMAC Pain as covariates. Kaplan-Meier median and quartiles will also be displayed.

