- Time to return to baseline is defined as the first week, of two consecutive non-missing weeks, where the WOMAC Pain score is  $\geq$  Baseline. For example, if a subject's WOMAC Pain scores are 5.0 (Baseline) and then:
  - 5.0 (Week 1), 4.8 (Week 2), 5.6 (Week 3), 5.0 (Week 4), 3.0 (Week 5), and 2.8 (Week 6), the return to baseline is Week 3 for this subject.
  - 5.6 (Week 1), 4.4 (Week 2), 4.2 (Week 3), 4.0 (Week 4), 3.0 (Week 5), and 2.0 (Week 6) (and then discontinued), the time to baseline pain for this subject is censored at Week 6.
  - 5.6 (Week 1), 6.0 (Week 2), 5.4 (Week 3), 4.6 (Week 4), and 4.4 (Week 5), the return to baseline is Week 1 for this subject.
  - 4.4 (Week 1), 5.2 (Week 2), Missing (Week 3), 5.6 (Week 4), and 3.2 (Week 5), the return to baseline is Week 2 for this subject.
  - Has 23 consecutive weeks of 2.0, and then 5.2 at Week 24, the time to baseline pain is censored at Week 24.
- Difference between treatment groups in area under the curve (AUC) of WOMAC Pain at Weeks 1–24
  - This analysis will be identical to that described for the key secondary endpoint for AUC of WOMAC Pain.
- Difference between treatment groups in AUC of average daily NPRS at Weeks 1–24
  - This analysis will be identical to that described for the key secondary endpoint for AUC of WOMAC Pain, however no missing data imputation will be done for this endpoint.
  - Average daily NPRS at Week 1 is defined as the average of non-missing NPRS pain scores from Day 1 through 8. For subsequent Weeks, average daily NPRS is defined as the average of the 7 days of non-missing daily NPRS data, allowing for the 8-day Week 1 (for example, Week 2 would be Days 9 through 15).
- Difference between treatment groups in AUC of WOMAC Function, Stiffness and Total scores at Weeks 4, 8, 12, 16, 20 and 24
  - This analysis will be identical to that described for the key secondary endpoint for AUC of WOMAC Pain, however no missing data imputation will be done for these endpoints.
- Difference between treatment groups in OMERACT-OARSI strict responders at Weeks 4, 8, 16, 20 and 24

- This analysis will be identical to that described for the key secondary endpoint for OMERACT-OARSI strict responders at Week 12.
- Difference between treatment groups in PtGA at Weeks 4, 8, 12, 18 and 24
  - This analysis will be identical to the primary analysis.
- Difference between treatment groups in MDGA at Weeks 4, 8, 12, 18 and 24
  - This analysis will be identical to the primary analysis.

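### For average daily NPRS, SAP 4.3 fills sparse diary weeks with entries from earlier weeks, while SAP 3.8.2 uses that week's scores only and rules out imputation for the NPRS AUC

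*SAP*

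**What the plan says.** **SAP 4.3 (Missing Data)** applies to three diary series, one of which is NPRS: "daily pain (NPRS) for post-baseline weeks will be imputed in instances when less than 4 entries are available at a given week". The method is stated as follows: "Last observation carried forward (LOCF) will be applied to carry forward the most recent post-baseline diary entries so that 4 entries are made available". In the SAP's own example of a week holding one entry, "the 3 most recent entries from previous post-baseline weeks will be carried forward to compute a weekly average out of 4 days". A second example has three entries in the week and one carried forward.

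**SAP 3.8.2 (Additional Secondary Efficacy Endpoints)** treats NPRS differently in three places:

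- Weekly value: "Average daily NPRS at Week 1 is defined as the average of non-missing NPRS pain scores from Day 1 through 8". For later weeks, "average daily NPRS is defined as the average of the 7 days of non-missing daily NPRS data". The illustration given for Week 2 is Days 9 to 15, so the average belongs to a fixed calendar week. No minimum number of entries is set.
- AUC of average daily NPRS: the key secondary AUC method applies, "however no missing data imputation will be done for this endpoint".
- Change from baseline in average daily NPRS: "This analysis will be identical to the primary analysis". For that primary analysis SAP 3.7 says: "No imputation of missing data will be performed for this analysis".

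The opening of 4.3 sends the reader to 3.7, 3.8 and 4.5 for missing data in the primary and secondary endpoints, and presents its own bullets as additional considerations. Neither 4.3 nor 3.8.2 says which rule prevails for NPRS. SAP Section 5, which lists departures from the protocol, does not mention it.

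**The concern.** Two programmers could each follow a section of the SAP faithfully and produce different NPRS tables. The choice also affects interpretation. NPRS is analysed at every week from 1 to 24, so its main use is to show how pain changes over time. The documents expect change: Protocol 1.2.2 describes separation from vehicle lasting 8 to 12 weeks at the lower dose, and Protocol 2.1 expects the 25 mg dose to extend efficacy beyond 12 weeks.

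A week padded with earlier scores is pulled toward the earlier level. If pain has risen, the loss of effect is blunted; if pain has fallen, the improvement is blunted. The padded mean then enters the analysis as an ordinary observation, and the same daily scores count in more than one week, so the uncertainty of that value is understated. For the change-from-baseline analysis none of this is needed, since the planned MMRM accommodates a missing week under its missing-at-random assumption.

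**Working it through.** **Step 1. Inputs.** The threshold (4 entries) and the source of the filler (earlier post-baseline weeks) come from SAP 4.3. The rival definition (that week's non-missing scores) comes from SAP 3.8.2. The documents give no rate of missing diary entries.

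**Step 2. Share of the weekly mean that comes from earlier weeks.** With k entries in the week, and k below 4, the rule adds 4 − k earlier entries, so the carried-forward share is (4 − k)/4. With 4 or more entries it is 0. The SAP's two examples agree: 1 entry plus 3 carried gives 3/4, and 3 entries plus 1 carried gives 1/4.

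**Step 3. The two rules on the same diary.** Let c be the mean of the current week's entries and e the mean of the carried entries.

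- SAP 3.8.2: weekly value = c.
- SAP 4.3: weekly value = [k × c + (4 − k) × e]/4.
- Difference (4.3 minus 3.8.2) = (4 − k)/4 × (e − c).

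The scores below are assumed for illustration and are not in the documents.

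| Entries in week | Share from earlier weeks | 3.8.2 value (e = 3, c = 6) | 4.3 value (e = 3, c = 6) | 3.8.2 value (e = 6, c = 3) | 4.3 value (e = 6, c = 3) |
|---|---|---|---|---|---|
| 3 | 25% | 6.00 | 5.25 | 3.00 | 3.75 |
| 2 | 50% | 6.00 | 4.50 | 3.00 | 4.50 |
| 1 | 75% | 6.00 | 3.75 | 3.00 | 5.25 |
| 4 or more | 0% | 6.00 | 6.00 | 3.00 | 3.00 |

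**Step 4. Range.** The size in points depends on the assumed gap between earlier and current pain. For a gap of 1 point, the weekly value moves by 0.25, 0.50 or 0.75 with 3, 2 or 1 entries. For a gap of 3 points, it moves by 0.75, 1.50 or 2.25. These are shifts in one subject's value for one affected week. They are not shifts in the treatment difference.

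**Step 5. Weeks the rule leaves unclear.** Read literally, fewer than 4 includes 0, in which case the whole weekly value would come from earlier weeks. The rule is headed as covering intermittent missing data, which suggests that weeks after dropout are not filled, but neither case is spelled out. Week 1 has no earlier post-baseline week to draw on.

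**The case against.** The strongest defence is that the no-imputation statements sit at a different level. The NPRS AUC sentence says the method follows the key secondary WOMAC Pain AUC and then makes an exception. Protocol 11.7.2 plans imputation for that key secondary when a subject discontinues before Week 12, so the exception may switch off only dropout imputation and leave the diary fill in place. Likewise, the statement in SAP 3.7 can be read as concerning missing weekly outcomes in the MMRM. The SAP layers rules in this way elsewhere: SAP 4.5 scores WOMAC Pain with one item missing, although the primary analysis has no imputation. For NPRS change from baseline, the conflict with 3.7 arises only by cross-reference.

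This is a fair reading and it weakens the no-imputation clauses as evidence. It does not remove the conflict. The weekly definitions in 3.8.2 still use non-missing scores from that week, and an entry from an earlier week is not one of them. The WOMAC parallel is also limited, because that rule averages the remaining items of the same questionnaire and borrows nothing from an earlier week.

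Two further points for the defence stand. Only weeks with fewer than 4 entries are affected. Entry to the trial also requires at least 5 daily scores in each run-in week (Protocol 5.2, criterion 8), so sparse weeks may be uncommon, although follow-up completeness is not stated.

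A reader might infer that the contradiction covers all three diary series. It does not. The rescue medication text in 3.8.2 refers to 4.3 for its imputation, and the activity analysis is described as analogous. Both use ANCOVA rather than the MMRM, so the argument that the model already handles a missing week does not carry over to them.

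**Conclusion.** The contradiction is real for average daily NPRS and for that series only. Wherever a post-baseline week has 1 to 3 entries, and earlier and current scores differ, SAP 4.3 and SAP 3.8.2 give different weekly values, with 75% to 25% of the 4.3 value coming from earlier weeks. The shares follow from the SAP's text; the shifts in points rest on assumed scores.

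Two stronger conclusions are tempting and are not supported. The first is that the rule biases the NPRS treatment comparison by a known amount or in a known direction. It applies in both arms, the pull can go either way, and neither the rate of sparse weeks nor the weekly slope of pain is given, so the net effect cannot be computed. The second is that the trial's main conclusions are at risk. The primary endpoint and the key secondary hierarchy rest on WOMAC, so only additional secondary NPRS endpoints are affected. This should be corrected, but it does not threaten the primary result.

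**What to change.** Remove daily pain (NPRS) from the carry-forward rule in SAP 4.3. Compute weekly NPRS from that week's observed entries, as 3.8.2 already says, and leave a week with no entries missing, so that the MMRM handles it in the change-from-baseline analysis. State the same rule in 4.3 and 3.8.2. Because the AUC is not analysed by the MMRM, add a line on how the trapezoidal calculation treats an empty week. If a minimum number of entries is wanted for NPRS, state it explicitly: 3.8.2 sets none, and its 4-entry minimum is written for rescue medication.

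The cost is SAP wording. The downside is that a weekly value based on 1 to 3 entries is slightly noisier or, if a minimum is adopted, that a few more weekly values are missing. The change belongs before unblinding, when Protocol 11.1 requires the SAP to be final. If that point has passed, document which rule was used and report the other as a sensitivity analysis.

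Dropping carry-forward for rescue use and activity, or moving them from ANCOVA to the MMRM, is optional. It would be a preference of method, not the correction of a contradiction.
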